6.4.7 Gynecological Examination

A gynecological examination is performed at the Screening and Week 12 / Early Termination visits, and will include the following assessments: Visual Inspection of External Genitalia; Speculum Examination of Vagina; Speculum Examination of Cervix (if present); Bimanual Palpation of Uterus and Ovaries (if present); Breast Palpation; and Papanicolaou Exam (in subjects with a cervix, at Screening only).

The number and percentage of subjects with normal, abnormal not clinically significant and abnormal clinically significant results respectively will be summarized for each assessment at each visit by treatment group and overall.

The papanicolaou examination is conducted at the Screening visit only and the associated normal / abnormal not clinically significant / abnormal clinically significant result is recorded on the eCRF. These results will be summarized as described above. The smear samples are sent to the central laboratory, [REDACTED], for analysis, and the detailed results from the cytopathology reports will be listed only.

6.4.8 Endometrial Biopsy

An endometrial biopsy is performed in subjects with a uterus as a mandatory procedure at the Screening and Week 12 / Early Termination visits, and whenever the subject presents with vaginal bleeding at any other visit.

The slides from the endometrial biopsies will be sent to the central laboratory, [REDACTED] for evaluation. Three independent pathologists, who will be blinded to subject, treatment assignment and to each other's evaluations, will assess the endometrial biopsies obtained at the Week 12 / Early Termination visit plus 10% of the Screening slides and all slides diagnosed with hyperplasia or cancer. The slides from the Screening visit and from any visit where the subject presents with vaginal bleeding will be assessed by only the primary pathologist.

The primary pathologist will be from [REDACTED] and the other two pathologists will be from different institutions but will travel to [REDACTED] to evaluate the endometrial biopsies.

Each pathologist will provide their evaluation according to the following categories, which are ordered from best to worst diagnosis, i.e. atypical hyperplasia (carcinoma) is the most severe diagnosis, followed by complex hyperplasia, simple hyperplasia and benign endometrium accordingly.

Table 5: Histologic Characteristics of the Endometrium

0	No tissue
1	Tissue insufficient for diagnosis
2	Atrophic
3	Inactive
4a	Weakly proliferative
4b	Active proliferative
4c	Disordered proliferative
5a	Secretory - Cyclic type
5b	Secretory - Progestational type (including stromal decidualization)
6	Menstrual type
7	Simple hyperplasia without atypia
8	Simple hyperplasia with atypia
9	Complex hyperplasia without atypia
10	Complex hyperplasia with atypia
11	Carcinoma (specify type)

For any subject, the final diagnosis will be accepted as the concurrence of two of the three pathologists. If there is no agreement among the three pathologists, the most severe pathologic diagnosis will be used as the final diagnosis. The evaluations of all three pathologists must be verified by the CRA in order to be considered for final analysis.

If hyperplasia is diagnosed by the single safety reader for a subject who has bled while on study treatment, this diagnosis will be maintained for the efficacy/safety evaluation and the slides become part of the slide set given to the two other pathologists for reading.

The bullet points below specify how many pathologists will review the biopsy samples at each visit and how the final diagnosis of a sample will be programmatically derived at each visit.

- Screening Visit
 - Biopsy sample is mandatory.
 - Samples reviewed by Pathologist 1 only.
 - Final diagnosis = diagnosis of Pathologist 1
 - 10% of samples will also be reviewed by Pathologist 2 and Pathologist 3 **for QC purposes only**. The diagnoses of Pathologist 2 and Pathologist 3 will **not** be used in the determination of final diagnosis.

- All slides diagnosed with hyperplasia or cancer (categories 7, 8, 9, 10 or 11 from Table 5 above) by Pathologist 1 will also be reviewed by Pathologist 2 and Pathologist 3 **for QC purposes only**. The diagnoses of Pathologist 2 and Pathologist 3 will **not** be used in the determination of final diagnosis.
- Baseline, Week 3 and Week 8 Visits
 - Biopsy sample is only taken if the subject presents with vaginal bleeding at the visit, otherwise the eCRF is marked as Not Applicable.
 - Samples reviewed by Pathologist 1 only.
 - Final diagnosis = diagnosis of Pathologist 1
 - All slides diagnosed with hyperplasia or cancer (categories 7, 8, 9, 10 or 11 from Table 5 above) by Pathologist 1 will also be reviewed by Pathologist 2 and Pathologist 3 **for QC purposes only**. The diagnoses of Pathologist 2 and Pathologist 3 will **not** be used in the determination of final diagnosis.
- Week 12 / Early Termination Visit
 - Biopsy sample is mandatory.
 - Samples reviewed by Pathologist 1, Pathologist 2 and Pathologist 3.
 - Final diagnosis derived as follows:
 - If the subject presents with vaginal bleeding at the visit (as indicated by an answer of 'Yes' to the direct question on the eCRF) and Pathologist 1 diagnoses hyperplasia or cancer (categories 7, 8, 9, 10 or 11 from Table 5 above):
 - Final diagnosis = diagnosis of Pathologist 1, **regardless** of the diagnoses of Pathologist 2 and Pathologist 3, even if Pathologist 2 and Pathologist 3 concur on a different diagnosis, either more or less severe than that of Pathologist 1.
 - Otherwise:
 - If two of the three pathologists agree (i.e. diagnose the same category from Table 5 above), their agreed diagnosis is the final diagnosis.
 - If all three pathologists diagnose a different category from Table 5 above), the most severe diagnosis is taken as final diagnosis.

For summary purposes, the Baseline histologic result will be the final diagnosis from the Baseline visit if endometrial samples were taken due to the subject presenting with vaginal bleeding at that visit, or the final diagnosis from the Screening visit otherwise.

The number and percentage of subjects with each histologic characteristic will be summarized (according to the final diagnosis, as defined above) at each visit by treatment group and overall.

A table presenting the shift in result from Baseline to Week 12 / Early Termination (according to the final diagnosis) will also be presented by treatment group. For the shift table, the denominator of percentage will be the number of subjects in the Safety population in each treatment group.

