6.3.3 Endometrial Biopsy

Endometrial biopsy will be performed per the provided standard collection method. Samples are to be fixed and stored using directions supplied by the centralized laboratory. The investigator shall do his/her best to obtain endometrial tissue for analysis. The Investigator must record whether tissue was obtained, and send the tissue obtained to the centralized laboratory to be processed.

At the centralized laboratory, a single pathologist will assess the slides from the endometrial biopsies obtained at Screening (per the standardized criteria for determining hyperplasia, as detailed in *Blaustein's Pathology of the Female Genital Tract* (Kurman RJ, 2011) as well as any biopsies obtained if a subject experiences vaginal bleeding while on study drug. Three independent pathologists (from different institutions with independent fiduciary and organizational reporting), blinded to subject's treatment group and to each other's readings, will assess the endometrial biopsies obtained at the Week 12/Early Termination Visit. The concurrence of two of the three pathologists will be accepted as the final diagnosis. If there is no agreement among the three pathologists, the most severe pathologic diagnosis (i.e., atypical hyperplasia > complex hyperplasia > simple hyperplasia > benign endometrium) would be used as the final diagnosis. If hyperplasia is diagnosed by the single safety reader for a subject who has bled while on study drug, this diagnosis be maintained for the efficacy evaluation and the slides become part of the slide set given to the two other pathologists for reading.

Per the draft FDA guidance on estrogen and estrogen/progestin drug products to treat vasomotor symptoms and vulvar and vaginal atrophy symptoms (US Dept. Health and Human Services, 2003), the set of slides distributed to each of these pathologists for the end-of-study pathology review will incorporate control slides representing a randomly selected 10% of the screening normal slides and all slides from subjects excluded for the diagnosis of hyperplasia or cancer to insure quality control.

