Tables presenting the shift in result (low, normal, high) from Baseline (Screening) to Week 12 / Early Termination will also be presented for each laboratory parameter by treatment group. For the shift tables, the denominator of percentage will be the number of subjects in the Safety population in each treatment group.

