6.4.6 Transvaginal Ultrasound

A transvaginal ultrasound is performed at the Screening and Week 12 / Early Termination visits for subjects with an intact uterus, and will include assessments of endometrial thickness and pelvic pathology (ovaries, miomas, etc.).

The number and percentage of subjects with normal, abnormal not clinically significant and abnormal clinically significant results, respectively, will be summarized for each assessment at each visit by treatment group and overall.

A table presenting the shift in result (normal, abnormal not clinically significant, abnormal clinically significant) from Baseline (Screening) to Week 12 / Early Termination visit will also be presented for each assessment by treatment group. For the shift table, the denominator of percentage will be the number of subjects in the Safety population in each treatment group.

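### The SAP's endometrial safety derivations carry two conflicting severity orders, and the biopsy and ultrasound shift tables divide by a population that includes women without a uterus

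*SAP*

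**What the plan says.** **Severity order.** At Week 12/Early Termination three pathologists read each biopsy. SAP 6.4.8 takes the category on which two agree. If all three differ, it takes the most severe. It introduces the categories as ones "which are ordered from best to worst diagnosis, i.e. atypical hyperplasia (carcinoma) is the most severe diagnosis, followed by complex hyperplasia", with simple hyperplasia and then benign endometrium below. Protocol 6.3.3 has the same ranking, with no carcinoma class: "atypical hyperplasia > complex hyperplasia > simple hyperplasia > benign endometrium". In Table 5, code 8 is "Simple hyperplasia with atypia" and code 9, listed as worse, is "Complex hyperplasia without atypia".

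**Denominator.** SAP 6.4.8: "An endometrial biopsy is performed in subjects with a uterus as a mandatory procedure". SAP 6.4.6: "A transvaginal ultrasound is performed at the Screening and Week 12 / Early Termination visits for subjects with an intact uterus". Protocol 4.1.1 admits women after bilateral oophorectomy whether or not they have had a hysterectomy. Protocol 7.4 and 7.8.4 confine both summaries to women with an intact uterus. Yet the biopsy shift table is specified thus: "For the shift table, the denominator of percentage will be the number of subjects in the Safety population in each treatment group". SAP 6.4.6 says the same for ultrasound.

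**Two further rules in SAP 6.4.8.** Agreement means the same Table 5 category, and Table 5 includes code 0 (no tissue) and code 1 (insufficient tissue). The narrative, like protocol 6.3.3, keeps the single reader's hyperplasia diagnosis for a woman who bled at any time on treatment. The Week 12 derivation applies this only to bleeding at that visit, and there it overrides the two-of-three rule.

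**The concern.** Endometrial histology is a named safety endpoint for an estrogen product, and SAP 6.7 plans no data monitoring committee, so these tables carry weight. The final diagnosis is derived by program, yet two programmers following the same section could tabulate different diagnoses from the same three reads. If the order is settled after unblinding, the choice could be influenced by the results.

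The denominator makes any shift to an abnormal endometrium look rarer than it was among the women who could show one. The error always runs in that direction.

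**Working it through.** **1. Severity order.** Table 5 has 15 codes: 0, 1, 2, 3, 4a, 4b, 4c, 5a, 5b, 6, 7, 8, 9, 10, 11. The order is used only when all three reads differ, so the relevant sets number C(15,3) = 455.

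- *Table order:* 7 < 8 < 9 < 10 < 11.
- *Worded order:* simple (7) < complex without atypia (9) < atypical (8 and 10). Carcinoma (11) is either above the atypical class or, as the SAP sentence writes it, inside that class.
- *Assumption:* the ten codes below 7 keep their Table 5 order, since the wording gives none within benign endometrium.

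Different answer: {8, 9, x} with x any of the 11 codes from 0 to 7. The table gives 9 and the wording gives 8. That is 11 of 455. Example: reads 7, 8, 9.

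No unique worst code under the worded order:
- Carcinoma on top: {8, 10, x} with x not 11, so 15 − 3 = 12 sets.
- Carcinoma in the atypical class: {8, 10, x}, {8, 11, x} and {10, 11, x}, with x outside {8, 10, 11}, give 3 × 12 = 36. Adding {8, 10, 11} makes 37.

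The 11 sets and these further sets do not overlap. In every one of them the candidate final codes lie within 8 to 11, so the combined count of hyperplasia or cancer is the same whichever order is used.

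**2. Denominator.** The plan's group size reproduces: 57 / (1 − 0.18) = 69.5, rounded to 70 (SAP 6.1.4). Let h be the share without a uterus, which the documents do not give. For c cases the SAP reports c/70, against c/[70(1 − h)] among women with a uterus. The ratio is 1 − h, so the relative understatement is h. With c = 2, assumed for illustration, the SAP figure is 2/70 = 2.9%.

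| Assumed h | Women with a uterus | Percentage among them |
|---|---|---|
| 10% | 63 | 2/63 = 3.2% |
| 20% | 56 | 2/56 = 3.6% |
| 30% | 49 | 2/49 = 4.1% |

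Women with a uterus but without a result at both time points widen the gap, so h is a lower bound.

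**3. Codes 0 and 1.** Read literally, 0, 0, 7 is tabulated as no tissue, but 0, 1, 7 falls to the most-severe step and becomes simple hyperplasia. Two equal non-diagnostic codes with one read of hyperplasia or carcinoma (codes 7 to 11) give 2 × 5 = 10 patterns. In each, that read leaves the tabulated diagnosis unless the bleeding rule applies to it.

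**4. Bleeding rule.** The narrative trigger is bleeding at any time on treatment; the Week 12 trigger is bleeding at that visit. Where the Week 12 rule applies, Pathologist 1 reading 7 against 11 and 11 from the other two is tabulated as simple hyperplasia, although the narrative gives the two-of-three rule without exception. Protocol 6.3.3 keeps the single reader's diagnosis but does not say that a worse concurrence is disregarded.

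**The case against.** **The order conflict is narrow.** It concerns one adjacent pair and needs three different reads. Since the SAP derives by Table 5 category, table order is a natural programming default. This stands as a limit on size. The counts are read patterns, not probabilities, and randomised women with a uterus had already been cleared of hyperplasia at screening. But a default that contradicts the sentence introducing it, and the protocol, is not a specification.

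**The denominator is a disclosed convention.** SAP 6.4.5 uses it for laboratory shifts too: "For the shift tables, the denominator of percentage will be the number of subjects in the Safety population in each treatment group". The protocol says whose changes are summarised but names no percentage base. The by-visit tables use non-missing denominators under SAP 6.1.1 and already give a usable Week 12 percentage. The table shells are not in the public text, so a not-applicable row cannot be excluded. All of this is fair, but laboratory tests apply to every woman and these two assessments do not. A not-applicable row would leave the stated denominator unchanged. The SAP's general rules, to include subjects only where they have data and to use non-missing denominators, give way to the explicit shift-table sentence. Protocol 6.3.2 suggests that the screening ultrasound may establish whether a uterus is present, but the schedules and SAP 6.4.6 limit the examination to women who have one.

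**The last two items are not errors.** This is right. No text says whether a non-diagnostic read counts as a diagnosis, and a lone hyperplasia read is also outvoted in 2, 2, 7. The Week 12 bleeding rule is explicit and implements the protocol's instruction to keep the single reader's diagnosis. They are queries only.

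**Stronger readings.** A reader might infer that the hyperplasia rate itself depends on the severity order, that women without a uterus appear in the shift cells, or that the laboratory shift tables share the fault. The documents support none of these. The combined count is invariant to the order, women without a uterus enlarge only the denominator, and laboratory tests have no such restriction. Missing Week 12 results would dilute laboratory percentages as well, but that is a different issue.

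**Conclusion.** Two errors hold, both limited to descriptive safety tables; no efficacy conclusion is affected.

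1. The severity order is contradictory. Eleven of 455 all-different triples change final diagnosis. Twelve more (carcinoma on top) or 37 more (carcinoma within the atypical class) have no unique worst code under the worded order. The grade is affected, never the combined count of hyperplasia or cancer. These figures assume Table 5 order among the codes below 7 and say nothing about how often such reads occur.
2. Counts in the biopsy and ultrasound shift tables are right, but their percentages are understated in relative terms by at least the share of women without a uterus. The absolute size depends on that unknown share. The 10% to 30% range, the 2 cases and 70 treated women per group are assumptions.

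The treatment of codes 0 and 1 is a gap in a literal rule. The bleeding rule is a mismatch between passages. Both need clarification and carry less weight than the two errors.

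**What to change.** Before unblinding:

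1. State one complete severity order for all 15 Table 5 codes, with carcinoma and the ranking among the atypical codes placed explicitly, and reconcile it with protocol 6.3.3. Which order is right is a matter for the pathologists and the sponsor.
2. In the biopsy and ultrasound shift tables, use as denominator the women with a uterus and a result at both time points. The laboratory shift tables need no change on this ground.
3. State whether codes 0 and 1 can form a two-of-three agreement against a diagnostic read, and flag such cases.
4. Reconcile the bleeding trigger between protocol 6.3.3, the SAP 6.4.8 narrative and the Week 12 derivation, and reconcile the override with the two-of-three rule. Report any more severe concurrence alongside the tabulated diagnosis.

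The cost is SAP wording and derivation code, plus a clarification against protocol 6.3.3 for item 4. Slides, readers and data stay the same.

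### At Week 12, in a woman who presents with bleeding, a hyperplasia reading by Pathologist 1 displaces even a more severe diagnosis on which the other two pathologists agree

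*SAP*

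**What the plan says.** SAP 6.4.8 sets a general rule for endometrial histology: "For any subject, the final diagnosis will be accepted as the concurrence of two of the three pathologists". For three-way disagreement it adds: "If there is no agreement among the three pathologists, the most severe pathologic diagnosis will be used as the final diagnosis".

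The Week 12 / Early Termination derivation then carves out a bleeding branch. It applies when two conditions hold together:

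- "If the subject presents with vaginal bleeding at the visit (as indicated by an answer of 'Yes' to the direct question on the eCRF");
- "Pathologist 1 diagnoses hyperplasia or cancer (categories 7, 8, 9, 10 or 11 from Table 5 above").

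In that branch the final diagnosis is Pathologist 1's, "even if Pathologist 2 and Pathologist 3 concur on a different diagnosis, either more or less severe than that of Pathologist 1". All other Week 12 samples follow the general rule.

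Protocol 6.3.3 is shorter: "If hyperplasia is diagnosed by the single safety reader for a subject who has bled while on study drug, this diagnosis be maintained", after which the slides go to the two other pathologists. An earlier paragraph of SAP 6.4.8 repeats this in nearly the same terms. Neither says what happens when the other two find something worse. The explicit upward override appears only in the SAP's Week 12 derivation, and SAP 6.8 does not list it as a change from the protocol.

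The reporting follows the derived result: "The number and percentage of subjects with each histologic characteristic will be summarized (according to the final diagnosis, as defined above"). The shift table does the same.

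**The concern.** The bleeding branch works in two directions. Downwards, it stops two less severe readings from cancelling a hyperplasia diagnosis in a woman with a warning sign. That is cautious and easy to defend.

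Upwards, it discards a worse diagnosis, including one shared by two of three blinded readers. It also drops the plan's own safeguard that the most severe reading prevails when all three differ. For readings above Pathologist 1's, the woman who bleeds is therefore graded less cautiously than the woman who does not.

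Change in endometrial histology is a safety endpoint (Protocol 7.4) of a dose-ranging estrogen trial. What is at stake is the grade shown by arm in Tables 14.3.6.1 and 14.3.6.2. A carcinoma or atypia reading shared by two pathologists could be missing from both tables because the woman bled.

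**Working it through.** The plan gives no figure to reproduce. The check applies the Week 12 rule, with and without bleeding, to every possible set of readings.

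**Inputs.** SAP Table 5 has 15 categories (0, 1, 2, 3, 4a, 4b, 4c, 5a, 5b, 6, 7, 8, 9, 10, 11). Severity is first taken in that order. The bleeding branch needs Pathologist 1 in one of five categories (7 to 11), so there are 5 × 15 × 15 = 1,125 triads, written Pathologist 1/2/3.

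**Single cases**

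| Triad | Final, bleeding | Final, no bleeding |
|---|---|---|
| 7/2/2 | 7 | 2 |
| 7/11/11 | 7 (simple hyperplasia without atypia) | 11 (carcinoma) |
| 7/8/11 | 7 | 11 |
| 10/11/11 | 10 | 11 |

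The first row is the protective effect. The other three are downgrades.

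**Graded lower with bleeding.** Let *k* be the number of categories above Pathologist 1's and *m* the number below. Pathologists 2 and 3 agree on something worse in *k* triads. All three differ, with at least one reading worse, in *k*(*k* − 1) + 2*km* triads.

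| Pathologist 1 | k | m | Others agree on worse | All differ | Total |
|---|---|---|---|---|---|
| 7 | 4 | 10 | 4 | 12 + 80 = 92 | 96 |
| 8 | 3 | 11 | 3 | 6 + 66 = 72 | 75 |
| 9 | 2 | 12 | 2 | 2 + 48 = 50 | 52 |
| 10 | 1 | 13 | 1 | 0 + 26 = 26 | 27 |
| 11 | 0 | 14 | 0 | 0 | 0 |
| Sum | | | 10 | 240 | 250 |

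Of the 250, 4*k* summed over the rows = 16 + 12 + 8 + 4 = 40 include a no-tissue or insufficient-tissue reading.

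**Graded higher with bleeding.** This needs the other two to agree on something less severe: *m* triads per row, 10 + 11 + 12 + 13 + 14 = 60. The two rules differ in 250 + 60 = 310 triads.

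**Carcinoma lost.** For each of Pathologist 1 = 7, 8, 9 and 10, the non-bleeding result is 11 if both others read 11 (1 triad), or if one reads 11 and the other reads any of the 13 categories that are neither 11 nor Pathologist 1's (2 × 13 = 26). That gives 4 × 27 = 108, of which 4 have the other two agreeing.

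**Atypia or carcinoma lost (categories 8, 10, 11).** Pathologist 1 must read 7 or 9.

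- Reading 7: 3 agreeing, plus 26 (highest reading 11), 24 (highest 10) and 20 (highest 8) = 73.
- Reading 9: 3 agreeing (8/8, 10/10, 11/11), plus 26 and 24 = 53.
- Total 73 + 53 = 126, of which 6 have the other two agreeing.

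One of the six is 9/8/8. By Table 5 order it is not a downgrade, so 125 of the 126 lie within the 250.

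**Severity order.** Table 5 places simple hyperplasia with atypia (8) below complex hyperplasia without atypia (9). The prose order in the same section puts atypical above complex. Swapping 8 and 9 leaves 250, 60 and 108 unchanged. The tenth agreeing downgrade becomes 9/8/8 instead of 8/9/9, and the atypia-or-carcinoma count becomes 150. The 7/11/11 case is unaffected.

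**Hyperplasia-or-worse status.** Pathologist 1 is in categories 7 to 11 throughout the branch, so this status is lost in 0 of the 250 downgrades.

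**Table cell.** The rule is "For the shift table, the denominator of percentage will be the number of subjects in the Safety population in each treatment group". With the planned 70 per arm, one such woman moves the carcinoma cell from 1/70 (1.4%) to 0/70.

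**The case against.** The rule is deliberate. The SAP spells out both directions, and the protocol's instruction to keep the safety reader's diagnosis can naturally be read as final in either direction. That reading stands as possible, so a reader should not infer that the SAP contradicts the protocol. The same words fit a floor equally well, and the protocol sentence does not settle which is meant.

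Bleeding-triggered samples at Baseline, Week 3 and Week 8 also take Pathologist 1's diagnosis, so Week 12 might seem merely consistent with them. But at those visits the plan has Pathologist 1 alone read for diagnosis, and the others see hyperplasia or cancer slides only for quality control. At Week 12 all three readings are diagnostic.

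A reader might set 250 downgrades against 60 protected triads and infer that the branch harms more than it protects. The documents do not support that: the patterns carry no probabilities. Only 10 of the 250 involve the other two agreeing on something worse.

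Finally, the consequence is limited. The tables are descriptive. SAP 6.1.1 requires central-laboratory data to be listed, and Listing 16.2.10 covers biopsies, so individual readings may remain visible, although its layout is not shown. This stands, and it keeps the point minor.

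**Conclusion.** The point holds as a minor flaw in a safety derivation. The upward override has no protective purpose, runs against the plan's own most-severe rule, and can under-grade a carcinoma or atypia on which two of three pathologists agree. Its reach is 250 of 1,125 patterns, 10 of them with the other two agreeing on the more severe category. How often any of these would occur cannot be derived from the documents.

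A reader might infer that a cancer could vanish from the safety results. That goes too far. The woman is still tabulated with hyperplasia or worse; only the grade in two descriptive tables changes, and no efficacy conclusion is affected.

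The counts assume that the derivation is programmed as written, with severity in Table 5 order except where the alternative is shown. The 1/70 illustration assumes that all 70 planned women in the arm enter the Safety population.

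**What to change.** In the Week 12 / Early Termination part of SAP 6.4.8, replace the whole bleeding-branch result, including the words that set aside Pathologists 2 and 3 and the clause on more or less severe concurrence, with:

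> Final diagnosis = the more severe of Pathologist 1's diagnosis and the result of the two-of-three / most-severe rule below; a less severe concurrence of Pathologists 2 and 3 does not lower Pathologist 1's diagnosis.

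Also state which of categories 8 and 9 ranks as more severe. Under Table 5 order 9/8/8 stays at 9, so a two-reader finding of atypia is still displaced; under the prose order it becomes 8.

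Leave the bleeding condition, the non-bleeding branch and the rules for the other visits as they are.

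The new rule changes exactly the 250 downgraded triads, keeps the result of all 60 protected ones, and never falls below Pathologist 1's diagnosis or the ordinary rule. It needs no new biopsy, reading, visit or eCRF field. The one further cost is that, if the protocol sentence is read literally as final, the change should be recorded in SAP 6.8.

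### At Week 12 the SAP tests pathologist agreement on exact Table 5 codes, so one hyperplasia reading prevails over two benign readings that differ only in sub-type

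*SAP*

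**What the plan says.** Protocol 6.3.3 has three blinded pathologists read each Week 12 / Early Termination biopsy: "The concurrence of two of the three pathologists will be accepted as the final diagnosis". Failing that, the worst diagnosis counts, on a four-level ranking: "i.e., atypical hyperplasia > complex hyperplasia > simple hyperplasia > benign endometrium) would be used as the final diagnosis". Benign endometrium is one level there.

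SAP 6.4.8 repeats the majority principle ("For any subject, the final diagnosis will be accepted as the concurrence of two of the three pathologists") and names the same four levels in words, with benign endometrium again as one. The readers, however, score on Table 5: "Each pathologist will provide their evaluation according to the following categories, which are ordered from best to worst diagnosis". Table 5 has 15 rows:

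- 0 and 1: no tissue or insufficient tissue
- 2, 3, 4a, 4b, 4c, 5a, 5b and 6: eight benign sub-types
- 7 to 11: hyperplasia and carcinoma, treated by the SAP as one group ("categories 7, 8, 9, 10 or 11 from Table 5 above")

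The derivation for Week 12 has two branches. If the woman is bleeding at the visit and Pathologist 1 reads hyperplasia or cancer, that reading stands, "even if Pathologist 2 and Pathologist 3 concur on a different diagnosis, either more or less severe than that of Pathologist 1". In every remaining case (the Otherwise branch) the rule reads: "If two of the three pathologists agree (i.e. diagnose the same category from Table 5 above), their agreed diagnosis is the final diagnosis". With three different codes, "the most severe diagnosis is taken as final diagnosis".

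The result feeds the histology summary and the shift table (SAP Tables 14.3.6.1 and 14.3.6.2). SAP 6.8, which lists changes from the protocol, does not mention the level at which agreement is tested.

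**The concern.** In the Otherwise branch, whether a lone hyperplasia reading prevails depends on something unrelated to hyperplasia: whether the other two readers chose the same benign sub-type. The most-severe fallback is a tie-break for real disagreement, yet benign sub-typing alone can trigger it. Change in endometrial histology is a named safety endpoint for an estrogen (Protocol 7.4), and hyperplasia counts are small in arms of about 70, so a diagnosis created by the derivation rule would be visible in the tables.

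A second problem concerns the fallback itself. Table 5 is said to run from best to worst, but it puts simple hyperplasia with atypia (8) below complex hyperplasia without atypia (9). Protocol 6.3.3, and the SAP's own sentence introducing Table 5, rank atypical above complex.

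**Working it through.** The documents give no figure to reproduce, so the check applies the rule as written.

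**Worked readings (Otherwise branch)**

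| Readings | SAP rule | Agreement on protocol levels |
|---|---|---|
| 2, 3, 7 | 7, simple hyperplasia | benign, two of three |
| 2, 2, 7 | 2, atrophic | benign, two of three |
| 8, 9, 2 | 9, complex without atypia | all differ; atypical is worst, so 8 |
| 0, 0, 7 | 0, no tissue | not defined by the protocol |

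Rows 1 and 2 contain the same lone hyperplasia reading and give opposite results. Row 3 shows the ordering conflict. Row 4 shows that two non-diagnostic readings outvote a diagnosis.

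**Count of combinations.** With one reading in codes 7-11 and two in the eight benign codes, there are 3 × 5 × 8 × 8 = 960 ordered triples. The benign codes differ in 3 × 5 × 8 × 7 = 840, and all of these become hyperplasia or carcinoma under the SAP rule. On grouped levels none do. The ratio 840/960 = 87.5% counts combinations; it is not an expected frequency.

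**Expected size.** Take a truly benign biopsy and three independent readers. Let p be the chance that a reader falsely calls hyperplasia, and d the chance that two benign readings differ in sub-type.

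- SAP rule: 3p(1-p)²d + 3p²(1-p) + p³
- Grouped levels: 3p²(1-p) + p³

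Neither p nor d is in the documents. Assumed: p = 0.5%, 1% or 2%. For d, assume a sub-type mix of 50/30/15/5% and a reader who reproduces the true sub-type with probability r and otherwise draws from the mix. Then d = (1-r²)(1-0.365), because 0.5² + 0.3² + 0.15² + 0.05² = 0.365. With r = 0.9, 0.75 and 0.6, d is 12%, 28% and 41%.

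Example, p = 1% and d = 12%: 3 × 0.01 × 0.9801 × 0.12 + 0.000298 = 0.0038, or 0.38%.

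| p | SAP, d = 12% | SAP, d = 28% | SAP, d = 41% | Grouped |
|---|---|---|---|---|
| 0.5% | 0.19% | 0.42% | 0.62% | 0.007% |
| 1% | 0.38% | 0.85% | 1.2% | 0.03% |
| 2% | 0.81% | 1.7% | 2.5% | 0.12% |

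For 70 women the extremes are 70 × 0.00186 = 0.13 and 70 × 0.0248 = 1.7 false diagnoses, against 0.005 and 0.08 on grouped levels. Widening d to 10-50% gives 0.16-3.0%, or 0.11 to 2.1 women per 70. All per-arm figures are upper bounds: they assume that every woman has a uterus and a diagnostic sample, whereas hysterectomized women are eligible and Table 5 provides for failed samples.

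**The case against.** **No protocol breach.** Protocol 6.3.3 does not define the level of concurrence. Its four levels appear only in the parenthesis that ranks severity for the fallback, and Protocol 7.8 leaves analysis detail to the SAP. Since readers score on Table 5, agreement on a Table 5 code is a legitimate reading. This stands. A reader might infer that the SAP contradicts the protocol; the text supports only a poor fit on the level of agreement. The order of codes 8 and 9 is a separate matter and does conflict with the stated ranking.

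**The rule is conservative.** For an estrogen, erring towards hyperplasia may be preferred, as in the bleeding branch. But the Otherwise branch lets two identical benign codes outvote one hyperplasia reading. Caution that applies only when benign sub-types differ is not a coherent safety rule.

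**Size.** The 87.5% weights all codes equally, including secretory and menstrual types in postmenopausal women, and should not be read as a rate. The error rates are assumptions. This stands.

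**Bias between arms.** A reader might infer a threefold excess on estriol by setting 12% sub-type disagreement on placebo against 41% on estriol (0.38% against 1.2%). In the model above, that contrast comes from making blinded readers less reproducible on estriol slides (r of 0.6 instead of 0.9), for which nothing in the documents gives a reason. Holding r = 0.75 and shifting the mix from 70/20/8/2 to 50/30/15/5 moves d from (1-0.5625)(1-0.5368) = 20% to 28%, about 1.4-fold, and that shift is itself hypothetical.

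**Consequence.** Histology is summarized descriptively, with no test or threshold, and the minimal effective dose rests on the efficacy gatekeeping. Endometrial Biopsy Listing 16.2.10 is already planned, so discordant readings should be traceable.

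**Conclusion.** The point holds as a defect in a stated derivation rule. In the Otherwise branch, benign sub-type disagreement alone can turn one hyperplasia reading into the final diagnosis, and the Table 5 order can select the wrong worst diagnosis on the protocol's ranking. Under the assumed error rates, false final hyperplasia is about 0.2-2.5% per biopsied woman, against 0.01-0.12% on grouped levels: at most about 0.1 to 1.7 women per arm of 70. At the low end this is negligible; at the high end it would show in a safety table. The calculation assumes independent readers and truly benign tissue.

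The documents do not support three stronger conclusions: that the SAP's level of agreement breaches the protocol, that the active arms would be affected more than placebo (possible, but not shown), or that one or two such diagnoses would decide how a dose is judged. The change is still worth making, because it is cheap and removes an avoidable artefact. The bleeding branch is outside this point.

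**What to change.** Before unblinding, amend the Otherwise branch of SAP 6.4.8:

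1. Map each reading to the Protocol 6.3.3 levels: codes 2-6 benign endometrium; 7 simple hyperplasia; 9 complex hyperplasia; 8 and 10 atypical hyperplasia. Place carcinoma (11) explicitly at the top, since the SAP text now brackets it with atypical hyperplasia.
2. Judge two-of-three concurrence on these levels, and use the most severe level only when all three differ.
3. State how codes 0 and 1 count, so that non-diagnostic readings cannot outvote a diagnosis.
4. Base Tables 14.3.6.1 and 14.3.6.2 on the level, with the Table 5 sub-type as a secondary description.
5. Flag in Listing 16.2.10 every biopsy with any single hyperplasia or carcinoma reading.
6. Record the level of agreement in SAP 6.8.

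The cost is SAP wording and a few lines of derivation code, with no new readings or data. The small downside is that isolated hyperplasia readings would appear in the listing and no longer in the summary and shift tables; the flag keeps them in view.
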